5.0 Subjects

Subjects are males age 50 to 85 undergoing elective spine surgery at Maine Medical Center who have surgery scheduled at least 5 days following enrollment, and are seen preoperatively at MMP Neurosurgery and Spine (MMP NSS).

5.1 Inclusion

- Male patients 50 to 85 years old
- Undergoing elective spine surgery at least 5 days after enrollment
- Preop visit done at MMP Neurosurgery and Spine
- Surgery to be done at Maine Medical Center

5.2 Exclusion

- Currently on tamsulosin or other alpha-adrenergic blocking drug
- Allergy to tamsulosin
- Allergy to lactose
- Serious or life-threatening allergy to sulfa drugs
- Emergent procedure
- Patients with spinal trauma, spinal infection or spinal cord tumor
- Patients with pre-existing indwelling urinary catheter
- Patients with a diagnosis of orthostatic hypotension, or orthostatic hypotension as defined by one or more of the following:
 - decrease in systolic blood pressure ≥ 20 mm from sitting to standing
 - decrease in diastolic blood pressure ≥ 10 mm from sitting to standing,
 - clinical symptoms of orthostatic hypotension upon standing (faintness, lightheadedness, vertigo)
- History of prior urethral or bladder surgery
- History of prostatectomy or other prostate surgery
- Patients with renal failure
- Non-English speaking
- Scheduled for cataract surgery within two weeks of study drug dosing

- Unable to provide informed consent (e.g. severe dementia)

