6.2 Outpatient procedures

After patient consent is obtained, all study patients will undergo a non-invasive post-void bladder scan via portable ultrasound to measure PVR. In addition, study staff will obtain a modified International Prostate Symptom Score (IPSS), a short survey to measure baseline lower urinary tract symptoms[17].

At this time, patients will also have orthostatic blood pressure measurements taken as follows:

- BP and pulse taken while patient is laying down and sitting
- BP and pulse taken after patient goes from sitting to standing

If patient meets definition of having orthostatic hypotension as described in 5.2 Exclusion Criteria, he will be excluded from study participation. A record of all patients screened and excluded for this reason will be kept with study documents. After PVR, BP and IPSS, patient will be given prescription for 7 days of study drug. Patient will be instructed to begin once daily evening administration of study drug five days prior to surgery, and to continue self-medication up to and including the night before surgery. Patients will record study drug administration on a drug diary card, given by office staff. Patient will be instructed to keep two doses at home for possible dosing after surgery, depending on discharge date. Patient and office providers will be blinded to the assigned medication.

Computer-generated 1:1 randomization (without blocking) will be done by the MMC pharmacy, which will place a seven day supply of tamsulosin 0.4 mg or placebo in sequentially numbered envelopes corresponding to study ID prior to study start. Study drug will be kept in and dispensed from locked cabinet in research coordinator's office. Study staff will access locked cabinet and pull next available envelope to give to consented patient. Study ID number will be logged into study binder kept in locked cabinet.

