6.5 Postoperative considerations

Post-operative care of study patients will include orders for the MMC Acute Retention Protocol, as follows:

- If patient has not voided after 4 to 6 hours or is uncomfortable, a bladder scan is done.
- Straight catheterization is done if bladder scan volumes are greater than 300 to 500 cc (defer if patient is known to chronically retain high volumes and is not uncomfortable).

All patients with POUR will be treated as deemed necessary by the medical team. Treatment of any patient that has POUR will not be guided or constrained by this study.

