8.0 Outcome

8.1 Primary Outcome

The primary outcome measure will be post-operative urinary retention, defined as the need for post-operative urinary catheterization for acute retention as defined by the MMC Acute Retention Protocol, or re-catheterization in those patients who leave the operating room with an indwelling catheter.

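### Section 5.2 excludes men with an indwelling catheter but not men who already catheterize intermittently, so some preoperative retention can be counted as POUR

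*Combined protocol and SAP*

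**What the plan says.** The only exclusion in section 5.2 that concerns catheter use is "Patients with pre-existing indwelling urinary catheter". Three other bullets bear on bladder emptying: "Currently on tamsulosin or other alpha-adrenergic blocking drug", "History of prior urethral or bladder surgery" and "History of prostatectomy or other prostate surgery". Renal failure is also listed. Neither 5.1 nor 5.2 mentions intermittent catheterization, chronic retention or a high baseline residual.

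Section 6.2 says that after consent "all study patients will undergo a non-invasive post-void bladder scan via portable ultrasound to measure PVR", but attaches no eligibility cut-off to the result.

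Section 8.1 defines the primary outcome as "the need for post-operative urinary catheterization for acute retention as defined by the MMC Acute Retention Protocol", and adds re-catheterization of men who leave the operating room with a catheter in place. The retention protocol is in section 6.5: "If patient has not voided after 4 to 6 hours or is uncomfortable, a bladder scan is done". Straight catheterization follows above 300 to 500 cc. The same bullet tells staff to defer it in a man known to retain high volumes chronically, provided he is comfortable. No section says how a man's usual intermittent catheterization is classified once he is postoperative.

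**The concern.** A man with an indwelling catheter presumably cannot show new retention that calls for a catheter, although the protocol gives no reason for excluding him. Much the same applies to a man who catheterizes himself intermittently before surgery, yet he can be enrolled. If he has not voided at 4 to 6 hours and the scan is above the threshold, he may be catheterized and counted as POUR, although this is his preoperative state and not something that arose after surgery.

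If such events occur equally in both arms, they raise both rates by the same amount and pull the risk ratio toward 1. The sample size has almost no reserve on its stated test, so even a few such events take power below 80%. A secondary outcome is also touched. A man who never voids spontaneously has no time to first void, and section 10.3 analyzes that time by t-test and linear regression with no rule for him.

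**Working it through.** **Inputs.** From section 10.2: control rate 0.170, tamsulosin rate 0.085, two-sided 0.05, 80% power, continuity-corrected chi-square, 264 per group. Not in the documents, so assumed: the share *c* of enrolled men who use intermittent catheterization (0.5% to 2%), and the probability *s* that such a man scores the endpoint (0.5 or 1, equal in both arms).

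**Step 1: reproduce the plan's figure.** With mean rate 0.1275 and difference d = 0.085, the uncorrected size is

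n0 = [1.960 × √(2 × 0.1275 × 0.8725) + 0.842 × √(0.17 × 0.83 + 0.085 × 0.915)]² / 0.085² = 240.5.

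The continuity correction gives n = (n0/4) × [1 + √(1 + 4/(n0 × d))]² = 263.5, so 264 per group, as stated. The odds ratio is (0.085/0.915)/(0.17/0.83) = 0.454, also as stated. Exact enumeration of the corrected test (summing the binomial probabilities of all result pairs whose statistic exceeds 3.841) gives 80.8% power at 264 per group. This is the baseline below.

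**Step 2: add the affected men.** If they come on top of the planning rates:

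- control rate = 0.17 × (1 − c) + c × s
- tamsulosin rate = 0.085 × (1 − c) + c × s

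For c = 1%, s = 1: 0.1683 + 0.0100 = 0.1783 and 0.08415 + 0.0100 = 0.09415, so the risk ratio is 0.528. For c = 1%, s = 0.5: 0.1733 and 0.08915, so the risk ratio is 0.514.

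| Assumed share c | Men per arm (264 × c) | Power if half score | Power if all score |
|---|---|---|---|
| 0 | 0 | 80.8% | 80.8% |
| 0.5% | about 1 | 79.9% | 79.2% |
| 1% | about 3 | 78.9% | 77.6% |
| 2% | about 5 | 77.0% | 74.4% |

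**Step 3: two variations.** (a) The center's 17% may already contain such men; the documents do not say. The control rate then stays at 0.17, and only the remaining events are halved: tamsulosin rate = (0.17 − c × s)/2 + c × s = 0.085 + c × s/2. At c = 1% this is 0.0875 with half scoring (power 77.9%) and 0.090 with all scoring (power 74.8%). (b) Section 10.3 plans chi-square tests without naming a continuity correction. On the uncorrected test, power is 84.4% at baseline and 81.5% at c = 1% with all scoring.

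**Step 4: who can still score.** Section 8.1 requires acute retention as the retention protocol defines it, so routine self-catheterization is not in itself an event. The deferral in 6.5 needs two conditions together: that the man is known to retain high volumes and that he is comfortable. Three routes to the endpoint remain: he is uncomfortable; staff do not know him as a retainer; or he leaves the operating room with a catheter and is re-catheterized, a route for which 8.1 states no exception.

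**The case against.** A reader might infer that any man who self-catheterizes will score the endpoint whatever his arm. The documents do not support that. The deferral clause in 6.5 addresses chronic retention directly, and 8.1 takes in the retention protocol that contains it, so a comfortable man known to retain high volumes would not be catheterized under it. This part of the objection stands, and it is why the rows with all men scoring are a worst case.

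Nor does it follow that nothing else in 5.2 keeps such men out. The bullets on alpha-blockers, urological surgery and renal failure will remove some. They do not remove, for example, a man with a neurogenic bladder and none of those histories, and this is a spine-surgery population.

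Equal scoring in both arms is also an assumption. Section 2.0 describes tamsulosin as a treatment for outlet-obstruction symptoms that reaches steady state after 5 days, so in a man who catheterizes because of obstruction the drug might matter. Similarly, a man who catheterizes may still void partially and so have a first void.

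Finally, broad eligibility is defensible. Section 10.1 collects past medical history, residual volume, IPSS and perioperative catheterization. Where catheter use is in the history, these men could be set aside in a sensitivity analysis. That would help, but the plan neither asks about catheter use specifically nor specifies such an analysis.

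**Conclusion.** The eligibility gap is real and its effect is probably small. A man who uses intermittent catheterization can be randomized and may be counted as POUR because of his preoperative state. Whether he is counted depends partly on his comfort and on what staff know of him.

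At an assumed 1% share, power on the corrected test falls from 80.8% to between 78.9% and 77.6%, or to between 77.9% and 74.8% if the 17% already includes such men. The risk ratio moves from 0.50 to between 0.51 and 0.53. The true share is unknown, and the figures rest on equal scoring in both arms. Under that assumption the expected effect is dilution toward no difference. A reader might infer a risk of a false-positive result, but events that occur equally in both arms do not create one. Unblocked randomization could leave these few men unevenly split by chance, but that would favor neither arm systematically. This is a worthwhile clarification, not a threat to the trial's validity.

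**What to change.** Extend the section 5.2 bullet so that after "Patients with pre-existing indwelling urinary catheter" it continues: *or who use intermittent catheterization at the time of enrollment*. Ask this as a direct question at the enrollment visit, where the IPSS and residual volume are already taken, and before the study-drug envelope is pulled.

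The cost is one phrase, one question, the loss of a few enrollees from a pool of 670 to 680 potentially eligible men a year (section 10.2), and slightly narrower eligibility.

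If the sponsor prefers to keep these men, the alternative is to record baseline catheter use, state how it is classified under 8.1, and specify a sensitivity analysis without them. That keeps eligibility broad but leaves the dilution in the primary analysis.

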6.0 Procedures

6.1 Screening and Consent

Eligible male patients will be screened and offered the opportunity for voluntary participation in this study at the preoperative office visit or initial consultation. The research consent form will be reviewed with the patient, who will have up to 5 days before surgery to decide on participation. Patients can provide informed consent during the office visit or can choose to return to the office at least 5 days prior to surgery for consent and randomization. Consenting may be done by CITI-trained attending surgeon, PA, staff nurse or research nurse. Consenting process will be documented in patient chart, and copy of informed consent will be given to patient and also scanned into chart.

6.2 Outpatient procedures

After patient consent is obtained, all study patients will undergo a non-invasive post-void bladder scan via portable ultrasound to measure PVR. In addition, study staff will obtain a modified International Prostate Symptom Score (IPSS), a short survey to measure baseline lower urinary tract symptoms[17].

At this time, patients will also have orthostatic blood pressure measurements taken as follows:

- BP and pulse taken while patient is laying down and sitting
- BP and pulse taken after patient goes from sitting to standing

If patient meets definition of having orthostatic hypotension as described in 5.2 Exclusion Criteria, he will be excluded from study participation. A record of all patients screened and excluded for this reason will be kept with study documents. After PVR, BP and IPSS, patient will be given prescription for 7 days of study drug. Patient will be instructed to begin once daily evening administration of study drug five days prior to surgery, and to continue self-medication up to and including the night before surgery. Patients will record study drug administration on a drug diary card, given by office staff. Patient will be instructed to keep two doses at home for possible dosing after surgery, depending on discharge date. Patient and office providers will be blinded to the assigned medication.

Computer-generated 1:1 randomization (without blocking) will be done by the MMC pharmacy, which will place a seven day supply of tamsulosin 0.4 mg or placebo in sequentially numbered envelopes corresponding to study ID prior to study start. Study drug will be kept in and dispensed from locked cabinet in research coordinator's office. Study staff will access locked cabinet and pull next available envelope to give to consented patient. Study ID number will be logged into study binder kept in locked cabinet.

6.3 Inpatient procedures

On hospital admission, MMC pharmacy will be informed of patient's inclusion in DRIPS study, and will be directed to dispense appropriate study drug (based on study ID number) on first postoperative night and on postoperative day one. All members of care team will be blinded to study drug assignment.

Patients discharged before evening of postoperative day one will be instructed to take study drug as described in section 6.6 below, with instructions given to both patient and family member if present.

In cases of potential urinary retention, inpatient portable bladder scans will be performed by unit nurses, who have been trained in this procedure.

6.4 Bladder Scans

Outpatient bladder scans done at MMP NSS will be done with a portable bladder scanner (SRS Medical Uroscan), used only for study purposes. This totally non-invasive test uses ultrasound technology to create a three-dimensional image of the bladder and calculate volume based on this image. Immediately after patient voids, he will be instructed to lay in supine position. Ultrasound gel will be applied to external probe, which will be placed on abdomen and urine volume will be displayed on device.

Because bladder scan by ultrasound is not a standard practice at MMP NSS, a study staff of at least five office-based nurses and/or medical assistants (MAs) will be trained in the proper use of the bladder ultrasound device. Training will be done by a representative of the bladder scanner manufacturer, or a nurse educator from an inpatient unit with a high volume of bladder scans (e.g. PACU); a log of trained MMP NSS nurses and MAs will be maintained in the regulatory binder. A daily "on-call" schedule of the bladder scan team will be developed and accessible to study staff via an Outlook calendar. Once a patient has given informed consent, the on-call team member of the day will be contacted to perform the scan and record the results in the patients' study chart.

Bladder scans done on inpatients at MMC will be standard of care and will be done by nurses who are already trained in the procedure. Technique is identical to that described above. Various makes and models are in use at MMC, but all are portable, with similar mechanisms of action. This procedure is familiar to all floor nurses at MMC, so no additional training will be necessary.

6.5 Postoperative considerations

Post-operative care of study patients will include orders for the MMC Acute Retention Protocol, as follows:

- If patient has not voided after 4 to 6 hours or is uncomfortable, a bladder scan is done.
- Straight catheterization is done if bladder scan volumes are greater than 300 to 500 cc (defer if patient is known to chronically retain high volumes and is not uncomfortable).

All patients with POUR will be treated as deemed necessary by the medical team. Treatment of any patient that has POUR will not be guided or constrained by this study.

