3.2 Secondary Objectives

Secondary analyses will include

- Treatment difference in length of stay
- Treatment difference in time to first spontaneous void

- Relationship between preoperative post-void residual (PVR) and POUR
- Correlation of baseline IPSS and POUR
- Relationship between duration of surgery and POUR

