4.0 Design

The study is a prospective, double-blind, randomized, placebo-controlled trial. Subjects will be randomized 1:1 to receive either oral tamsulosin 0.4 mg or placebo, taken once each evening, beginning 5 days prior to surgery and continuing through the first postoperative day. The primary endpoint is met when the patient is able to spontaneously empty their bladder post-operatively, or needs to be catheterized with either a straight or indwelling urinary catheter for post-operative urinary retention, whichever occurs first.

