10.0 Analytic Methods

10.1 Data collection

Data will be collected prospectively by study staff in the office, at the bedside and through Epic chart review. A study ID will be assigned to each patient and study documents will all use this ID to collect data. Identifiable data will be stored separately. Baseline variables to be collected will include basic demographics, past medical history and medication list, PVR and IPSS. Operative data will include type and duration of surgery, fluid intake, medications given, and any perioperative urinary catheterization. Data will be recorded postoperatively will include fluid balance, need for urinary catheterization, pain medication and adverse events.

All data will be recorded on a data collection sheet (see attached data sheet). PVR and IPSS done in the MMP NSS office will also be recorded on separate forms (see attached PVR and IPSS forms), which will be linked to the primary data collection sheet. These data sheets will be stored in a locked and secure area of the study coordinator's office.

RedCap, a HIPAA-compliant database, will be used to store all information after it is collected. Data entry and access will only be allowed to research coordinator and Principal Investigator.

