10.3 Randomization

To evaluate the success of randomization, characteristics of patients in the treatment and control groups will be compared using t-tests or their non-parametric equivalents, as appropriate, for continuous variables and chi-square tests or Fisher's exact tests, as appropriate, for categorical variables. The primary outcome, incidence of POUR, will be compared across groups using chi-square tests. If large baseline imbalances between groups are found, a secondary analysis will be performed using a logistic regression model, with POUR as the outcome variable, treatment group as the predictor of interest, and imbalanced patient characteristics as confounding variables. Secondary objectives examine the relationship between other factors and POUR and will be analyzed similarly. Length of stay and time to first void will be analyzed as continuous variables, using t-tests and linear regression models.

REFERENCES

1. Wu, A.K., A.D. Auerbach, and D.S. Aaronson, *National incidence and outcomes of postoperative urinary retention in the Surgical Care Improvement Project*. Am J Surg, 2012. **204**(2): p. 167-71.
2. Baldini, G., et al., *Postoperative urinary retention: anesthetic and perioperative considerations*. Anesthesiology, 2009. **110**(5): p. 1139-57.
3. Boulis, N.M., et al., *Urinary retention following routine neurosurgical spine procedures*. Surg Neurol, 2001. **55**(1): p. 23-7; discussion 27-8.
4. Jung, H.J., et al., *Postoperative urinary retention following anterior cervical spine surgery for degenerative cervical disc diseases*. Clin Orthop Surg, 2013. **5**(2): p. 134-7.

5. Gandhi, S.D., et al., *Patient and surgical factors associated with postoperative urinary retention after lumbar spine surgery*. Spine (Phila Pa 1976), 2014. **39**(22): p. 1905-9.
6. Burger, D.H., et al., *Prevention of urinary retention after general surgery: a controlled trial of carbachol/diazepam versus alfuzosine*. J Am Coll Surg, 1997. **185**(3): p. 234-6.
7. Hooton, T.M., et al., *Diagnosis, prevention, and treatment of catheter-associated urinary tract infection in adults: 2009 International Clinical Practice Guidelines from the Infectious Diseases Society of America*. Clin Infect Dis, 2010. **50**(5): p. 625-63.
8. Scott, R.D. *The Direct Medical Costs of Healthcare-Associated Infections in U.S. Hospitals and the Benefits of Prevention*. 2009 [cited 2015 November 24, 2015].

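### Does the plan leave open how a man whose catheterisation is deferred for known chronic retention is coded, and does this distort the PVR-POUR analysis?

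*Combined protocol and SAP*

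**What the plan says.** Section 8.1, the labelled primary outcome, counts as POUR the post-operative need for "urinary catheterization for acute retention as defined by the MMC Acute Retention Protocol". It also counts re-catheterisation in men who leave the operating room with a catheter.

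Section 6.5 sets out that protocol. The scan rule is: "If patient has not voided after 4 to 6 hours or is uncomfortable, a bladder scan is done". Straight catheterisation follows above a volume of 300 to 500 cc, with the instruction to "defer if patient is known to chronically retain high volumes and is not uncomfortable".

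Section 4.0 describes the endpoint in other words. A man reaches it once he "is able to spontaneously empty their bladder post-operatively, or needs to be catheterized with either a straight or indwelling urinary catheter" because of retention, whichever comes first.

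Section 3.2 lists "Relationship between preoperative post-void residual (PVR) and POUR" among the secondary objectives, with a similar one for IPSS. On their analysis, section 10.3 says: "Secondary objectives examine the relationship between other factors and POUR and will be analyzed similarly". Section 5.2 excludes "Patients with pre-existing indwelling urinary catheter" but sets no upper limit on PVR. Section 10.1 names neither deferral nor post-operative scan volume. It refers to an attached data sheet, which is not among the documents, and says: "Data will be collected prospectively by study staff in the office, at the bedside and through Epic chart review".

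**The concern.** Three things make this look like a defect.

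- **No stated code.** Neither 4.0, 8.1 nor 10.3 says what a deferred man is. Section 8.1 speaks of the need for a catheter, not its receipt, so one chart abstractor might count a man above the scan threshold as POUR and another might not.
- **A mismatch with 4.0.** Unless he voided earlier, a man at the moment of deferral has neither emptied his bladder nor been judged to need a catheter.
- **Deferral is tied to the exposure.** Known chronic retention is close to what pre-operative PVR measures. If deferred men are non-events, those non-events would probably fall mainly among high-PVR men and could weaken the PVR-POUR association, and possibly the IPSS-POUR one.

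At stake would be the reading of two secondary associations and, if coding were left to chance, some power in the primary comparison.

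**Working it through.** **Step 1: read the definitions together.** Section 8.1 takes its meaning of acute retention from the MMC Acute Retention Protocol. Section 6.5 is the text of that protocol and includes the deferral clause. Where the protocol itself says to defer, there is no need for catheterisation as the protocol defines it. So:

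- deferred and never catheterised: not POUR;
- deferred and later catheterised for acute retention: POUR.

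Section 4.0 runs until whichever limb occurs first. Deferral is a point on the way, not a time at which the outcome is coded. The mismatch usually ends when he voids or is catheterised. It persists only if he voids without emptying, or does neither during follow-up.

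**Step 2: reproduce the plan's sample size (section 10.2).** Inputs: 17.0% against 8.5%, two-sided 0.05, 80% power, continuity-corrected chi-square. The formula gives 241 per group without the correction and 264 with it, which matches the plan. Corrected power at 264 per group is Φ[(d − 1/n − 1.96·se0)/se1], where d = 0.085, se0 = √(2 × 0.1275 × 0.8725/264) = 0.0290 and se1 = √((0.17 × 0.83 + 0.085 × 0.915)/264) = 0.0288. The result is 80.1%.

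**Step 3: primary comparison if a share f is deferred.** The documents give no f. Assume it is equal in both arms, with rates of 17% and 8.5% in all other men.

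- Coded not POUR: rates are 0.17(1 − f) and 0.085(1 − f).
- Coded POUR: rates are f + 0.17(1 − f) and f + 0.085(1 − f).
- Left out: n becomes 264(1 − f).

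| f (men of 528) | not POUR | POUR | left out |
|---|---|---|---|
| 0.5% (about 3) | 79.8% | 78.5% | 79.9% |
| 1% (about 5) | 79.6% | 76.9% | 79.6% |
| 2% (about 11) | 79.1% | 73.9% | 79.2% |
| 5% (about 26) | 77.5% | 65.2% | 77.8% |

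Under the section 8.1 coding the risk ratio stays at 0.500 for any f. At 2% coded as POUR it would be (0.02 + 0.085 × 0.98)/(0.02 + 0.17 × 0.98) = 0.1033/0.1866 = 0.55.

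**Step 4: PVR-POUR association.** The documents give no PVR distribution or association, so this is illustration only. Expected events are 264 × 0.17 + 264 × 0.085 = 67.32 of 528 (12.75%). Assume 10% of men have high PVR (52.8 men) and an odds ratio of 2.0. That gives 11.16 events among high-PVR men and 56.16 among the other 475.2.

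- *If k deferred men are regarded as hidden cases but coded non-events:* OR = [(11.16 − k)/(41.64 + k)]/(56.16/419.04). For k = 0, 1, 2 this is 2.00 (95% CI 0.98 to 4.10), 1.78 and 1.57. Leaving those men out gives 1.82 and 1.64, not 2.00.
- *If deferred men are non-cases, as 8.1 implies:* the planned 2.00 stands. Leaving out 1 or 2 gives [11.16/(41.64 − k)]/(56.16/419.04) = 2.05 or 2.10.

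Attenuation therefore appears only when deferred men are treated as true events, which is not the outcome that 8.1 defines. An analysis excluding them barely moves the estimate on either view.

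**The case for a change.** The strongest case for a change is that it would be cheap: one sentence in 8.1, one aligned sentence in 4.0 and a reported count of deferrals. The power table also shows that coding is not harmless if many men are deferred. At an assumed 2%, counting them as POUR would take power to 73.9%. It can therefore be argued that the code should be fixed beforehand, and that without a count a reader cannot tell whether deferral touched the PVR result.

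Part of this stands. No sentence states the code outright, the word need invites a second reading, and a claim that the primary result is the same under any coding would be too strong beyond a few men. But the unfavourable figures belong to a coding that 8.1 does not support, and the sentence proposed would only write down what 8.1 and 6.5 already give together. The PVR analysis concerns catheterised retention in every man because of 8.1 itself, with or without deferral, and the plan asks about POUR so defined. Whether deferral and scan volume are already collected cannot be judged without the data sheet, and the Epic chart review in 10.1 offers a further route to them.

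**Conclusion.** No change is called for. The gap is one of explicitness, and an analyst following 8.1 and 6.5 fills it in one way: not POUR unless later catheterised for acute retention. On that coding, with equal deferral in the arms, the risk ratio is unchanged and power falls by about one point at an assumed 2% deferred. Even that loss disappears if the centre's 17% rate already reflects the same deferral practice, which the documents do not state. Since care staff are blinded (section 6.3), there is no evident reason for deferral to bias the randomised comparison.

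The secondary associations keep the meaning that 8.1 gives them. Any weakening is relative to a broader kind of retention that the plan does not study, and its size cannot be derived from the documents. That deferrals will be few is a judgement from the exclusions in 5.2 and the joint conditions in 6.5, not a figure in the plan. Stating the number deferred when results are reported would be a courtesy to readers, but the results and conclusions would be sound without it.
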